The PLUNGER Stroke Trial

A comparison of cyclic manual direct aspiration thrombectomy (Plunger technique) vs. static manual direct aspiration thrombectomy for treatment of acute large vessel occlusion stroke with the Raptor Aspiration Catheter

Principle Investigator:

[name], PhD
Director of Vanderbilt Cerebrovascular Program
Associate Professor of Neurology and Neurosurgery
Vanderbilt University Medical Center
Nashville, TN

Study Summary

Title	A comparison of cyclic manual direct aspiration thrombectomy (Plunger technique) vs. static manual direct aspiration thrombectomy for treatment of acute large vessel occlusion stroke with the Raptor Aspiration Catheter
Short title	The Plunger Stroke Trial
Objective	To compare the efficacy and safety of cyclic manual direct aspiration thrombectomy (Plunger technique) vs static aspiration for direct aspiration thrombectomy with the Raptor Aspiration Catheter
Design	A randomized, controlled trial of the Plunger technique vs. static manual direct aspiration thrombectomy for treatment of acute large vessel occlusion stroke. At least one pass with aspiration is required.
Sample size	A sample size of 500 subjects will detect a 15% absolute difference in successful first pass rate between the two groups at 90% power.
Duration	With 20 sites, enrollment can be completed in one year (Sites to be decided)
Primary endpoint	First pass effect (FPE) defined as TICI 2c or 3 after the first attempt of direct aspiration thrombectomy
Safety endpoint	Rate of symptomatic intracranial hemorrhage (sICH)
Secondary endpoints	Overall rate of TICI 2b or 3 recanalization with Plunger vs. static aspiration Functional outcome at 90 days based on mRS assessment Rate of successful navigation of aspiration catheter to clot Rate of rescue treatment with stent-retrievers Rate of complete clot ingestion Recanalization rates with the two different sizes of Raptor Rate of recanalization by clot density on CT (hyperdense vs isodense)
Inclusion criteria	Acute ischemic stroke due to occlusion of the terminal ICA or M1 segment of the MCA Treatment can be initiated within 24 hours of symptom onset Age 18 years or older
Exclusion criteria	Evidence of acute intracranial hemorrhage prior to treatment Failure to obtain informed consent

Background

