For *static aspiration*, the VacLok syringe is opened to create suction on the clot for a minimum of one minute (some interventionalists may prefer a longer 'dwell time' to encourage more clot ingestion, which is fine). Once the syringe is locked open, a timer is used to ensure adequate timekeeping. Once at least 1 minute or more has passed, then the catheter is carefully withdrawn into the guide catheter and removed. The guide catheter is then thoroughly aspirated to clear any fragmented clot. The duration of aspiration will be reported on the case report form (CRF). Other syringes or devices for aspiration may be introduced during the trial at the discretion of the steering committee.

Plunger Technique

The VacLok syringe is also used for the Plunger technique. The catheter is navigated to the clot face and aspiration is applied by drawing the syringe plunger back. However, the syringe is not locked, but instead the plunger is repeatedly pulled back and then released in a cyclic fashion [[Froehler, JNIS 2023](#)]. There is no need to cycle slowly, as seen in the how-to video. Operators may wish to pull the plunger more quickly than it is released, though our *in vitro* studies have shown that there is always negative pressure at the catheter tip and therefore no risk of 'pushing' the clot. Although obvious, it is important to note that when the plunger is released it should not be actively pushed forward as this could push the clot out of the catheter and into the distal vasculature.

When using the Plunger technique in the trial, active plunging must be performed for at least 30 s at a time, with pauses of no more than 30 s. When paused, the syringe must be locked in the fully open / full vacuum position. Total aspiration time, including active plunging and static vacuum pauses, must be at least one minute (one cycle of plunging). As with static aspiration, some surgeons may prefer to use a longer total aspiration time, which is acceptable. The VacLok syringe must then be locked in the full vacuum position before the catheter is removed in a fashion identical to that described above for the static aspiration technique.

Rescue treatment

Rescue therapy may be provided to the subject at the discretion of the study investigator. In the event that aspiration thrombectomy fails to achieve successful reperfusion (defined as TICI \geq 2b) after at least one attempt, any other FDA-approved thrombectomy device may be used by the study physician.

Training

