The Investigator is required to report all SAEs within 72 hours after first learning of the event. The primary method of reporting SAEs will be through the eCRFs. All SAEs will also be reported to the local IRB.

Site selection

Potential clinical sites will be assessed to ensure the investigator and his/her staff have the facilities, expertise required for the study and ability to conduct the study according to the clinical protocol.

To participate in this trial a clinical site must have, at a minimum, the following:

- 24/7 stroke interventional capabilities
- CT-based acute stroke imaging protocols (MRI is not acceptable)
- Ability to support timely data collection via an Internet-based EDC system
- Resources for conducting the informed consent process
- Willingness to adhere to the study protocol

Angiographic core lab

The procedural angiograms will be submitted by each site with all subject identifiers removed and only the assigned subject study number on the images. Each angiogram will be blindly assessed by the core lab for:

- Reperfusion score after first pass
- Reperfusion after final aspiration pass
- Reperfusion at end of procedure

Oculus Imaging, LLC, will serve as the core lab. The core lab services will include:

1. Trial Specific Website Design

- a. We will customize a user accessible website on our server specifically for the requested study. All imaging aspects of the study will be managed through this site.
- b. The primary functions of the site include electronic image submission, de-identification, and analysis.
- c. The website may also allow users or sponsors to review subject images and the dynamic trial reports as needed.
- d. Our study websites are secure, HIPAA, FDA, (CFR part 11) and E-Union compliant. Daily backups are performed.
- e. Studies are stored in at least two separate off-site archive sites.
- f. After launch of the trial website, any requested changes to the data collection for this trial may require a database change. Such requests would be reflected in a new version of the trial guidelines. Database changes may require revalidation of the trial imaging reports and additional fees may apply.

2. Imaging Protocol

- a. Oculus Imaging will write the Imaging Guidelines detailing imaging modalities to be used, imaging acquisition protocols, and procedures for image transfer.

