- a. A board-certified radiologist will interpret all images as required by the protocol. All reads will be interpreted in a blinded fashion. [name] would be the primary reader unless the sponsor requests a different physician.
- b. Summary images and image interpretations will be uploaded to the study-specific server site. All reads will be immediately available to the sponsors. Images and any interpretation data can be reviewed by site users as required by the protocol.
- c. The core lab will select images of interest during review. These will be immediately available for review by the sponsor or sponsor's designee from any web enabled device.
- d. The sponsor or any sponsor designee will have access to the entire imaging dataset once it has been validated for HIPAA compliance via download from our server. Our standard imaging turn-around time is 14 days from submission.

6. Imaging Data Reporting

- a. All imaging data collected during the trial will be saved on our secure database.
- b. Images and draft imaging reports are available via secure web access.
- c. These may be downloaded in PDF or excel format. These may also be downloaded in csv format to allow importing into other EDC systems.

Study Management and Oversight

Vanderbilt University Medical Center (VUMC) will serve as the coordinating center for this study. The VUMC team will be responsible for:

- Study protocol development and amendments
- Informed consent templates and revisions
- IRB approvals and correspondence
- Site initiation and training materials
- Case Report Forms (CRFs) and data collection tools
- Monitoring reports and audit documentation
- Adverse event and protocol deviation reporting
- Regulatory compliance (e.g., certifications, CVs, signature pages)
- Communication logs with participating sites
- Final study report and data safety monitoring documentation

Institutional review boards

The site investigator must submit this clinical protocol and subject informed consent form to the appropriate IRB. The study will not start at a clinical site and subjects will not be enrolled until a copy of written and dated approval/favorable opinion has been issued by the site.

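### The protocol opens core-lab reads of the primary endpoint to the sponsor as they are made, and no rule restricts who may tabulate first pass effect by arm before database lock

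*Protocol*

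**What the plan says.** All references are to the protocol.

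- **The endpoint.** Objective and endpoints defines FPE as TICI 2c or 3 after the first aspiration attempt, scored by the core lab. The list of core-lab assessments includes the first-pass score.
- **Sponsor access.** Angiographic core lab, item 5 (Image Interpretations), says "All reads will be immediately available to the sponsors". It adds that "The sponsor or any sponsor designee will have access to the entire imaging dataset once it has been validated for HIPAA compliance". Item 6 (Imaging Data Reporting) puts draft reports on the web and says "These may also be downloaded in csv format to allow importing into other EDC systems".
- **Running reports.** Item 1 (Trial Specific Website Design) says "The website may also allow users or sponsors to review subject images and the dynamic trial reports as needed".
- **Site access.** Item 5 says "Images and any interpretation data can be reviewed by site users as required by the protocol". This is conditional, and no other section requires such a review.
- **Timing.** Item 5 says "Our standard imaging turn-around time is 14 days from submission". The Study Summary says "With 20 sites, enrollment can be completed in one year".
- **Power to change the trial.** Study Management and Oversight gives amendments to the coordinating centre. Aspiration syringe and technique says "Other syringes or devices for aspiration may be introduced during the trial at the discretion of the steering committee".
- **Interim review.** The DSMB paragraph, under Institutional review boards, assigns the regular review of safety and efficacy data to the DSMB, along with advice on continuing, modifying or ending the study.

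**The concern.** In an open-label trial, the usual safeguard is that the people who run it do not see accumulating results by arm. Here the reads that make up the primary endpoint are released one by one, while the protocol leaves room for amendments and for new aspiration devices during enrolment. According to the Background section, the protocol's authors also developed the technique under test.

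Someone who knows how FPE is running by arm may be influenced when deciding on an amendment, a device introduction or how hard to encourage sites. That is operational bias. It can arise without any intent and is hard to disprove afterwards. A positive result could then be challenged because the people steering the trial were able to see it forming.

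**Working it through.** The protocol gives no figure on this point, so the check is mainly a reading of the text. It asks whether each step from a core-lab read to an arm-level comparison is open, and whether any section closes it.

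1. **Is the released read the primary endpoint?** Yes. The first-pass score is both a listed core-lab output and the endpoint definition.
2. **Is it released during enrolment?** Yes. Sponsor access is immediate once a read exists, and reads are due 14 days after submission. The only gate on bulk access is the HIPAA check. No section holds reads back until lock.
3. **Can a read be tied to a patient?** Yes. The opening of Angiographic core lab keeps the subject study number on the images.
4. **Can a patient be tied to an arm?** Yes, for anyone with access to the study database. Randomization is done in REDCap. Data collection includes a plunging-duration field that applies only to the Plunger arm. Under Electronic Data Capture and Monitoring, the coordinating centre oversees REDCap.
5. **Is anyone other than the core-lab reader described as blinded?** No.
6. **Can the same people alter the trial?** The coordinating centre writes amendments, and the steering committee may add aspiration devices. Sample size calculation also words 500 as a minimum total and gives no maximum.
7. **Is the sponsor the same team?** Not stated. This is the one step that must be assumed.

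**How much would be visible.** Inputs are 500 patients, 52 weeks and a read lag of 2 weeks. Even accrual is assumed.

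- Accrual: 500 / 52 = 9.6 per week.
- Visible at the end of enrolment = 500 × (1 − L/52), where L is the total lag in weeks from procedure to read.

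| Assumed upload delay | L | Visible |
|---|---|---|
| none | 2 | 500 × (1 − 2/52) = 481 (96%) |
| 4 weeks | 6 | 500 × (1 − 6/52) = 442 (88%) |
| 8 weeks | 10 | 500 × (1 − 10/52) = 404 (81%) |

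The upload delays are assumptions, because the protocol sets no submission deadline. Accrual weighted towards the end would lower these counts. Even accrual over a longer period would raise them: 18 months, or 78 weeks, with L = 2 gives 500 × (1 − 2/78) = 487.

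**A second route.** Data collection also has sites enter their own TICI score after each pass, immediately after the procedure, in the same REDCap database. That field has no core-lab lag. A site-read version of FPE by arm could therefore be tabulated even if the core-lab reads were closed.

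**The case against.** **The sponsor may not be the coordinating team.** This stands as a qualification. The protocol never identifies the sponsor, so the overlap is an inference, and the point is conditional on it or on data sharing between the two.

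**Sites do not have open access.** A reader might infer that every site can browse core-lab reads during enrolment. The text does not support that. Site review is tied to what the protocol requires, and nothing requires it; the website wording is only permissive. Operators also know the arm and see their own angiograms live, so a later core-lab read adds little about their own patients.

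**The reader is blinded.** True, and no biased scoring is shown. Blinding does not, however, address unplanned looks.

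**This is vendor text, and the rules may sit elsewhere.** Much of the section reads like a service description, and imaging and reading guidelines, a DSMB charter or an SAP may exist. The informed consent section also mentions graded REDCap access. But the protocol grants the access in plain terms, and no section applies graded access to allocations or outcomes. An SAP does not normally set permissions on a core-lab website.

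**The type I error.** A reader might infer that repeated looking inflates the false-positive rate, for example to about 14% with five equally spaced unadjusted looks. That figure assumes the trial stops at the first p below 0.05. The protocol plans no such action and gives the sponsor no efficacy stopping rule, so the figure does not measure this flaw.

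**Some supposed harms do not follow.** Consent precedes randomization, so selective approach of patients would change who is enrolled in both arms, not the contrast between them. No section gives the sponsor or sites a route to revise a read.

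**Conclusion.** The point holds in a limited form. The protocol expressly releases the primary-endpoint reads to the sponsor during enrolment, leaves the link to arm available in the coordinating centre's database, and nowhere restricts tabulation of FPE by arm before lock. If the sponsor is, or shares data with, the coordinating team, a running comparison outside the DSMB is possible.

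The exposure is large: most primary outcomes would be readable before enrolment ends, about 480 of 500 at the upper end under even one-year accrual and same-day upload, and about 400 with an eight-week upload delay. The resulting bias cannot be quantified from the document.

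The protocol permits such looks; it does not say that anyone will make them. There is no contradiction in the text and no error in the planned analysis. This is a conduct safeguard that should be put in place before enrolment, because it cannot be restored afterwards.

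**What to change.** 1. In Angiographic core lab, items 1, 5 and 6, state that core-lab TICI reads, draft reports and dynamic reports are withheld from the sponsor, coordinating-centre investigators, steering committee and sites until database lock. During the trial the core lab sends only image-quality and completeness queries.
2. In the DSMB paragraph or Electronic Data Capture and Monitoring, state that before lock only the DSMB and the statistician preparing its reports may tabulate FPE by arm. This must cover both the core-lab reads and the site-assessed TICI in REDCap; closing the core-lab route alone would leave the second route open.
3. State who the sponsor is, so that the restriction has a clear addressee.

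The cost is a permission setting on the core-lab website, a matching restriction on REDCap reports and a few sentences of protocol text. The small downside is that the sponsor and sites lose live feedback on reads. Sample size, endpoint and analysis do not change.
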